10.0.1 EXPANSION COHORT: EVALUATION DURING TREATMENT/INTERVENTION

Tests to be performed day 1 of each cycle of brentuximab vedotin

- History and physical exam
- CBC (may be drawn within 24 hours pre-treatment)
- Comprehensive metabolic panel
- ESR

- Cytokine levels (one 8.5 mL SST speckled red top tube - IL-10, IL-6, IL-1, TNF α): *****cycle 1 only**
- Modified Total Neuropathy Score (mTNS) and European Organization for Research and Treatment of Cancer (EORTC) quality of life questionnaire for chemotherapy-induced peripheral neuropathy (CIPN-20): ***** cycle 3 only**

Tests to be performed day 8 and 15 of each cycle of brentuximab vedotin

- History and physical exam
- CBC (may be drawn within 24 hours pre-treatment)

Tests to be performed at the completion of 3 cycles of brentuximab vedotin:

- FDG-PET/CT (1-7 days after the last dose of brentuximab vedotin). All studies will be obtained on dedicated PET/CT cameras. Patients must fast for 6 hrs prior to PET imaging, but intake of water or other non-caloric beverages is encouraged. When the patient arrives at one of the nuclear medicine imaging sites, a fingerstick blood glucose measurement will be obtained; patient with blood glucose levels > 200mg/dl are ineligible. Approximately 12 mCi of 18F FDG will be injected intravenously. Following an approximately 60-80 min uptake time, CT and PET images will be obtained from skull base to upper thigh using standard clinical imaging protocols. For a given patient, all serial PET/CT scans will be obtained on the same camera model.
- CT chest, abdomen, pelvis (1-7 days after the last dose of brentuximab vedotin)

Within 1 week of last dose of SGN-35 (+/- 4 days)

- Hemoglobin A1c
- Cytokine levels (one 8.5 mL SST speckled red top tube - IL-10, IL-6, IL-1, TNF α)
- Modified Total Neuropathy Score (mTNS) and European Organization for Research and Treatment of Cancer (EORTC) quality of life questionnaire for chemotherapy-induced peripheral neuropathy (CIPN-20)
- Bone marrow biopsy (if BM was involved before treatment and post-SGN-35 PET scan is negative)

Interventions while receiving brentuximab vedotin (SGN-35)

Treatment days

Test/treatment	Pretreatment	1	8	15	22	29	36	43	50	57	64	71	72-78
SGN-35		x	x	x		x	x	x		x	x	x	
History and Physical		x	x	x		x	x	x		x	x	x	
CBC	x	x*	x*	x*		x*	x*	x*		x*	x*	x*	
Comprehensive Metabolic Panel	x	x				x				x			
ESR	x	x				x				x			

Uric acid	x												
Lactate dehydrogenase	x												
Creatinine clearance**	x												
Hemoglobin A1c	x												x
Serum β -HCG***	x												
Hep B, C, HIV	x												
Cytokines		x										x	
Neuropathy Questionnaire	x								x			x	
BM Bx	x												x****
FDG-PET/CT and CT CAP	x												x
Echo or MUGA	x												
PFTs	x												

*may be drawn within 24 hours pre-treatment; ** if creatinine >1.5; ***premenopausal females; ****if previously positive

The following applies to patients receiving augmented ICE:

- A CBC and basic metabolic panel will be obtained upon each admission for chemotherapy and a 12-hour urine collection for creatinine clearance will be obtained prior to receiving carboplatin. Other laboratory evaluations during admission for ICE chemotherapy may be performed at the discretion of the inpatient attending physician. When receiving ifosfamide, urine will be monitored for hematuria by urinalysis.

The following will be performed within 21 days following the completion of augmented ICE:

- CT scan of the chest, abdomen, and pelvis
- FDG-PET/CT scan
- Bone marrow biopsy (if BM was involved before treatment and post-ICE PET scan is negative)

11.0 TOXICITIES/SIDE EFFECTS

Brentuximab vedotin: Fatigue, fever, diarrhea, nausea, peripheral neuropathy, neutropenia, alopecia, rash

Ifosfamide: Alopecia, nausea and vomiting, hematuria, gross hematuria, CNS toxicity, infection, renal dysfunction, allergic reactions and at high doses, cardiotoxicity, and myelosuppression.

Carboplatin: Myelosuppression, nausea, vomiting, peripheral neuropathy, ototoxicity, hepatic toxicity, electrolyte abnormalities, hypomagnesemia, hypocalcemia, and allergic reactions.

Etoposide: Myelosuppression, mucositis, alopecia, nausea, vomiting, headache, fever, hypotension, anorexia, and allergic reactions. Possible secondary leukemia.

Mesna: Nausea, vomiting, diarrhea.

Neupogen® (Filgrastim): Bone pain; exacerbation of preexisting autoimmune disorders; transient and reversible changes in alkaline phosphatase, uric acid and LDH; peripheral edema.

Neulasta® (Pegfilgrastim): bone pain, flu-like symptoms, nausea/vomiting, adult respiratory distress syndrome, sickle cell crises, splenic rupture (rare)

Placement of leukapheresis catheter: pneumothorax, deep venous thrombosis, infection, and bleeding.

12.0 CRITERIA FOR THERAPEUTIC RESPONSE/OUTCOME ASSESSMENT

Criteria for interim FDG-PET/CT assessment

Patients enrolled in this study will receive salvage treatment with brentuximab vedotin and those who achieve FDG-PET/CT normalization will proceed directly to ASCT without receiving standard salvage chemotherapy such as ICE or DHAP. Because this treatment strategy represents, for some patients, a departure from standard practice, or de-escalation of treatment, stringent criteria are required to designate those most appropriate for avoiding ICE chemotherapy. A five-point scale for assessing response on interim FDG-PET/CT scans, referred to as the “London criteria”, was developed by international experts in Nuclear Medicine and Oncology for use in diffuse large B cell lymphoma and HL¹⁷ and validated for use as interim assessment in HL patients.¹⁸ The 5-point scale is displayed in the following table.

Score	FDG-PET/CT scan result
1	No uptake above background
2	Uptake \leq mediastinum
3	Uptake $>$ mediastinum but \leq liver
4	Uptake moderately more than liver uptake, at any site
5	Markedly increased uptake at any site or new sites of disease

The score on this scale used to define a normal or abnormal scan depends upon the particular clinical strategy planned. For example, when escalation of treatment is planned based upon FDG-PET/CT results, defining an abnormal FDG-PET/CT by a score of 4 or 5 is appropriate to avoid overtreating patients. Conversely, when de-escalation of treatment is planned based upon FDG-PET/CT results, defining a persistently abnormal FDG-PET/CT by a score of 3, 4, or 5 is appropriate in order to avoid undertreating patients.

For the purpose of this study, a score of 1 or 2 will be considered a “normal” FDG-PET/CT scan because de-escalation of treatment is anticipated. All scores (1 through 5) will be recorded for each FDG-PET/CT scan and scans will be reviewed by either [name] or [name].

Progression free survival (PFS) and overall survival (OS) will be calculated from the time of initiation of brentuximab vedotin.

The response criteria developed by the International Harmonization Project for response assessment in lymphoma will be used to define complete response, partial response, and progression of disease in this study¹⁹. The definitions for response are detailed in the table below.

Table 2. Response Definitions for Clinical Trials					
Response	Definition	Nodal Masses	Spleen, Liver	Bone Marrow	
CR	Disappearance of all evidence of disease	(a) FDG-avid or PET positive prior to therapy; mass of any size permitted if PET negative (b) Variably FDG-avid or PET negative; regression to normal size on CT	Not palpable, nodules disappeared	Infiltrate cleared on repeat biopsy; if indeterminate by morphology, immunohistochemistry should be negative	
PR	Regression of measurable disease and no new sites	≥ 50% decrease in SPD of up to 6 largest dominant masses; no increase in size of other nodes (a) FDG-avid or PET positive prior to therapy; one or more PET positive at previously involved site (b) Variably FDG-avid or PET negative; regression on CT	≥ 50% decrease in SPD of nodules (for single nodule in greatest transverse diameter); no increase in size of liver or spleen	Irrelevant if positive prior to therapy; cell type should be specified	
SD	Failure to attain CR/PR or PD	(a) FDG-avid or PET positive prior to therapy; PET positive at prior sites of disease and no new sites on CT or PET (b) Variably FDG-avid or PET negative; no change in size of previous lesions on CT			
Relapsed disease or PD	Any new lesion or increase by ≥ 50% of previously involved sites from nadir	Appearance of a new lesion(s) > 1.5 cm in any axis, ≥ 50% increase in SPD of more than one node, or ≥ 50% increase in longest diameter of a previously identified node > 1 cm in short axis Lesions PET positive if FDG-avid lymphoma or PET positive prior to therapy	> 50% increase from nadir in the SPD of any previous lesions	New or recurrent involvement	

Abbreviations: CR, complete remission; FDG, [¹⁸F]fluorodeoxyglucose; PET, positron emission tomography; CT, computed tomography; PR, partial remission; SPD, sum of the product of the diameters; SD, stable disease; PD, progressive disease.

13.0 CRITERIA FOR REMOVAL FROM STUDY

Patients will be followed on study until progression of disease or 2 years following autologous stem cell transplant.

The following patients will be removed from study:

- Patients who have progression of disease while on treatment. These patients may be offered alternate treatments.
- Patients who develop unacceptable toxicity.
- Patients who request that they be removed from study. This will not compromise the care they receive at this institution.
- Patients who are non-compliant with treatment or follow-up.

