2.0 OBJECTIVES AND SCIENTIFIC AIMS

Primary objectives

1. Determine the rate of FDG-PET/CT normalization following salvage therapy with brentuximab vedotin (SGN-35) alone or followed by augmented ICE chemotherapy

Secondary objectives

1. Rate of FDG-PET/CT normalization with respect to the presence of previously determined prognostic factors: extranodal disease, bulk \geq 5cm, relapse within previously radiated fields, relapse within 1 year of initial treatment, and presence of B symptoms at relapse
2. Determine overall response rate (CR and PR) rate to brentuximab vedotin alone
3. Toxicity from brentuximab vedotin alone and followed by augmented ICE chemotherapy
4. Evaluate progression free survival (PFS) and overall survival (OS) with this treatment program and their correlation with: Δ SUVmax, expression of CD68, FoxP3, and TIA-1 by immunohistochemistry, serum cytokine levels, and the clinical factors listed in secondary objective #1.
5. Determine number of CD34 cells collected following this treatment program.

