As an additional criterion, we require that at least 7 out of the total 46 patients (15%) achieve FDG-PET/CT normalization after SGN-35 to call this new regimen a success. The purpose of this criterion is to exclude the situation that all patients may fail SGN-35 (i.e., persistent PET abnormalities) and hence must receive ICE salvage therapy, yet accidentally pass the above two-stage design. The threshold 15% was chosen because the previous phase I data show that about 30% of patients may achieve CR with SGN-35, and thus we believe it would be clinically meaningful to require at least 15% of patients to achieve PET normalization after SGN-35 to call it a success.

For the secondary objectives, we will report the stratified FDG-PET/CT normalization rates as sample proportions with their confidence intervals. Overall response rate to SGN-35 alone will be reported similarly. Toxicities will be summarized and tabulated. PFS and OS (see

definition in Section 12) will be analyzed using standard survival tools such as Kaplan-Meier estimation, log-rank tests and/or Cox regression models to incorporate various factors (such as Δ SUVmax, CD68, FoxP3, TIA-1, serum cytokine, etc.) and assess their correlation with PFS and/or OS. Competing risks analysis will be conducted if competing risk(s) exists (such as death without progression). Lab results including CD34 cell yield following mobilization will be reported as summary statistics.

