16.0 DATA MANAGEMENT ISSUES

A Research Study Assistant (RSA) will be assigned to the study. The responsibilities of the RSA include project compliance, data collection, abstraction and entry, data reporting, regulatory monitoring, problem resolution and prioritization, and coordination of the activities of the protocol study team.

The data collected for this study will be entered into the Clinical Research Database (CRDB). Source documentation will be available to support the computerized patient record.

Data to be collected will include:

1. Patient related features:

- age
- sex

2. Disease related features

- prior therapy
- disease status- relapsed vs. primary refractory
- results of all tests related to the study
- disease status at long-term follow-up

3. Treatment related

- duration of treatment
- stem cell yields
- response to treatment
- toxicities of treatment

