17.2.1 SAE reporting information to Seattle Genetics

- **Reporting Timeframe:** The Principal Investigator will report to Seattle Genetics Drug Safety by [contact] or [contact] (USA only toll free) any Serious Adverse Event (SAE) that occurs in a study subject within 24 hours of first awareness of the event.
- **Reporting Forms:** The Principal Investigator will report such SAEs using the Seattle Genetics SAE Report Form or the approved local regulatory form SAEs should be reported as soon as they are determined to meet the definition, even if complete information is not yet available.
- **Reporting Period:** The reportable events that are subject to this provision are those that occur from the start of administration of the first dose of the Product through thirty (30) days after discontinuation of the Product. SAEs occurring more than thirty (30) days after discontinuation of the Product that are assessed by the Investigator as related to the Product should also be reported.

- **Follow-up Information:** The Principal Investigator will assist Seattle Genetics in investigating any SAE and will provide any follow-up information reasonably requested by Seattle Genetics.
- **Regulatory Reporting:** Reporting an SAE to Seattle Genetics does not relieve the Principal Investigator conducting the study of the responsibility for reporting it to the FDA, local regulatory authority, or IRB/IEC as required.

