18.0 INFORMED CONSENT PROCEDURES

Before protocol-specified procedures are carried out, consenting professionals will explain full details of the protocol and study procedures as well as the risks involved to participants prior to their inclusion in the study. Participants will also be informed that they are free to withdraw from the study at any time. All participants must sign an IRB/PB-approved consent form indicating their consent to participate. This consent form meets the requirements of the Code of Federal Regulations and the Institutional Review Board/Privacy Board of this Center. The consent form will include the following:

1. The nature and objectives, potential risks and benefits of the intended study.
2. The length of study and the likely follow-up required.
3. Alternatives to the proposed study. (This will include available standard and investigational therapies. In addition, patients will be offered an option of supportive care for therapeutic studies.)
4. The name of the investigator(s) responsible for the protocol.
5. The right of the participant to accept or refuse study interventions/interactions and to withdraw from participation at any time.

Before any protocol-specific procedures can be carried out, the consenting professional will fully explain the aspects of patient privacy concerning research specific information. In addition to signing the IRB Informed Consent, all patients must agree to the Research Authorization component of the informed consent form.

Each participant and consenting professional will sign the consent form. The participant must receive a copy of the signed informed consent form.

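### Overall survival is a planned secondary analysis, but on-study follow-up ends at progression and nothing provides for vital status or OS censoring afterwards

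*Combined protocol and SAP*

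**What the plan says.** Section 2.0, secondary objective 4, is to "Evaluate progression free survival (PFS) and overall survival (OS) with this treatment program" and to relate both endpoints to the change in SUVmax, tissue markers, serum cytokines and clinical factors.

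Section 14.0 refers the reader elsewhere for the "definition in Section 12) will be analyzed using standard survival tools such as Kaplan-Meier estimation, log-rank tests and/or Cox regression models". Section 12.0 supplies one sentence: "Progression free survival (PFS) and overall survival (OS) will be calculated from the time of initiation of brentuximab vedotin". That fixes the time origin. It names no event and no censoring date.

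Section 13.0 sets the follow-up: "Patients will be followed on study until progression of disease or 2 years following autologous stem cell transplant". It also removes patients for progression on treatment, unacceptable toxicity, non-compliance or their own request, and mentions no survival contact after removal.

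Four other places touch on later information:

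- Section 16.0 lists "disease status at long-term follow-up" as a data item.
- Section 17.2.1 limits routine SAE reporting to the drug supplier to events "from the start of administration of the first dose of the Product through thirty (30) days after discontinuation of the Product", with later events reported only if judged related.
- Section 14.0 adds: "Competing risks analysis will be conducted if competing risk(s) exists (such as death without progression".
- Section 18.0 says the consent form will cover "The length of study and the likely follow-up required".

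**The concern.** Follow-up to progression is enough for PFS but not for OS, which needs every patient observed to death or to a last date known alive, whether or not the disease has progressed. A patient whose observation stops at progression leaves the OS risk set just when the risk of death rises; Section 3.0 itself describes the outlook after a failed transplant as very poor. Such censoring is informative. If it happens, the Kaplan-Meier curve labelled OS describes only death without progression. Marker effects that act through progression would be attenuated, and a marker acting solely through progression would show no effect.

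The limit of 2 years after transplant is a different matter. It is administrative censoring and does not cause this bias.

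**Working it through.** **Is there a provision anywhere?** Section 16.0 names disease status, without vital status, date of death or a schedule. The supplier's SAE window closes 30 days after SGN-35 is discontinued, apart from related events. The competing-risks sentence gives death without progression as its example, not death after it. The consent form is not available for review and would not set an analysis rule. The documents therefore do not say that deaths after progression are ignored, and they do not say that they are collected.

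**Size if they are not collected.** The plan states no OS figure to reproduce, so this is an illustration.

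*From the documents.* Section 3.0 gives 5-year event-free survival of 75% with normalized pre-transplant imaging and 31% without. Section 14.0 gives normalization rates of 40% (null) and 60% (desirable). With a constant hazard in each group, survival at 2 of 5 years is the 5-year figure to the power 0.4: 0.75^0.4 = 0.891 and 0.31^0.4 = 0.626. Mixing gives 24-month PFS of:

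- 0.4 × 0.891 + 0.6 × 0.626 = 0.732
- 0.6 × 0.891 + 0.4 × 0.626 = 0.785

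This is a proxy from earlier ICE programs.

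*Assumed.* Death without progression by 24 months, d: 1%, 3%, 6% or 10%. Median survival after progression: 12, 18, 24, 36 or 60 months. With two PFS values this makes 40 scenarios.

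*Model.* Constant hazards per month:

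- total h = −ln(PFS)/24
- death without progression m = d·h/(1 − PFS)
- progression p = h − m
- death after progression g = ln 2/median

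True OS at 24 months = e^(−24h) + p·(e^(−24g) − e^(−24h))/(h − g). If every patient is censored at progression, Kaplan-Meier tends to e^(−24m).

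*One case in full* (PFS 0.732, d = 3%, median 24 months): h = 0.01299, m = 0.00146, p = 0.01154, g = 0.02888. True OS = 0.732 + 0.01154 × (0.500 − 0.732)/(0.01299 − 0.02888) = 0.732 + 0.169 = 0.901. The censored curve gives e^(−0.035) = 0.966, an overstatement of 6.5 points. Of 46 × 0.099 = 4.6 deaths, 46 × 0.03 = 1.4 are seen, so 70% are missed.

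| PFS, d, median (months) | True OS | Censored at progression | Deaths missed |
|---|---|---|---|
| 0.732, 1%, 12 | 0.867 | 0.988 | 92% |
| 0.732, 3%, 24 | 0.901 | 0.966 | 70% |
| 0.785, 6%, 36 | 0.908 | 0.935 | 35% |
| 0.785, 10%, 60 | 0.885 | 0.894 | 13% |

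*Over all 40 scenarios*, by the share of progressed patients followed to death:

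| Share followed | Overstatement of 24-month OS (points) | Median |
|---|---|---|
| None | 0.9 to 12.2 | 4.9 |
| Half | 0.4 to 5.5 | 2.3 |
| 80% | 0.2 to 2.1 | 0.9 |

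With none followed, 0.7 to 5.7 deaths per 46 patients are missed, out of 1.7 to 8.3 in total. At an assumed PFS of 0.50 (d = 1%, median 12) the gap reaches 24 points (0.745 against 0.986).

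*Death records without a censoring rule.* If deaths are entered whenever they become known but living patients are censored at progression, simulation (200,000 patients per scenario) shows OS biased downward by 0.4 to 1.1 points. Both parts of the fix are needed.

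*Markers.* With a hazard ratio of 2 on progression and 1.25 on death without progression, the OS hazard ratio is 1.28 to 1.87 with full follow-up and about 1.25 with censoring at progression.

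**The case against.** The strongest reply is that this is silence and not contradiction. Section 13 limits how long patients are followed on study; it does not say that OS is censored at progression. By convention OS means death from any cause, censored when last known alive, and a single center may learn of deaths from its own records. Section 17.2 requires SAEs to be reported to the IRB through the clinical research database with no stated end date, Section 16.1 provides for monitoring of follow-up, and the consent form may describe survival contact.

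This is why the point is conditional. It does not remove it. Section 17.2 sets no reporting window and does not require deaths to be captured once a patient is off study. Section 16.1 can monitor only the follow-up that the plan specifies. Neither sets a censoring date. Without one, two analysts could draw different OS curves from the same patients.

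The second objection concerns size, and much of it stands. The anchor is an event-free survival figure from earlier programs, used here as PFS from the first SGN-35 dose. The 40% and 60% are design hypotheses. The death rates are assumed, and the scenario spread carries no probability. Section 3.0 also says that about half of patients fail transplant, without a time horizon, so a PFS below 73% cannot be excluded. At OS of 90% with 46 patients, the 95% half-width is 1.96 × √(0.9 × 0.1/46) = 8.7 points, which exceeds the bias in 35 of the 40 scenarios. But a confidence interval displays sampling error; it does not display this bias, and more patients would not reduce it.

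**Conclusion.** The concern holds. The follow-up rule in Section 13 cannot support the OS and marker-OS analyses in Sections 2 and 14, and no available text repairs it. The upward direction is firm if deaths after progression go uncaptured. The size cannot be derived from the documents: about 1 to 12 points at 24 months with no capture, falling to about 2 points or less if 80% of progressed patients are followed, under the assumptions stated above. The primary PET conclusion, the go/no-go rules and PFS do not depend on it. It should be fixed because OS is a reported result and the repair is cheap. Confidence is medium, because actual practice at the site and the consent terms cannot be seen.

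**What to change.** - **Section 13:** separate the end of treatment from the end of follow-up. Collect vital status for all enrolled patients in both cohorts after progression or removal, unless consent to follow-up is withdrawn, up to a common data cut-off.
- **Sections 12 and 14:** define OS as time from the first SGN-35 dose to death from any cause, censored at the date last known alive and not at progression or removal.
- **Section 16:** add vital status, date of death and date last known alive to the data list.
- **Marker analyses:** label the OS results exploratory. Even with full capture, only about 2 to 8 deaths by 24 months are expected in 46 patients under these assumptions.
- **If this is not feasible:** report OS as descriptive, state that deaths after progression were not systematically captured, and rest the marker correlations on PFS.

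The cost is an amendment to four sections and periodic chart or telephone checks, with no added procedures. Section 3.0 reports 37 patients accrued by April 2013, so it must be checked that existing consent covers patients already removed. Those who refuse or cannot be reached stay censored. The change makes OS interpretable; it does not give the marker-OS analyses adequate power.
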